4.3.4. Description of visits

Periodicity of the procedures and assessments is also provided in Schedule of visits and procedures (see Table 1).

4.3.4.1. Visit 1 (Day 1)

Visit 1 (Day 1) includes screening, randomization and administration of the study products.

Before any study-related procedures are performed, the study nature and study-related potential risks should be explained to all study subjects and they should provide their informed consent. After informed consent is obtained, the following procedures will be carried out:

- collection of medical history;
- recording previous and concomitant therapy;
- collection of demographic data;
- recording 12-lead ECG results on which STEMI diagnosis was based

CONFIDENTIAL

Translation dated 27-Oct-2021

based on Russian Version 4.0 dated 02-Oct-2021

Page 41 of 98

- recording CAG results;
- evaluation of vital signs (BP, HR, RR, body temperature);
- physical examination;
- body weight measurement (using hospital bed, if available);
- determination of absolute neutrophil count (in local laboratory);
- urine pregnancy test for females with childbearing potential (test strips);
- blood collection for hematology and blood chemistry, determination of hsCRP, BNP and NT-pro-BNP;
- Echo-CG (this procedure is permitted to be done within 24 hours from the moment of randomization);
- evaluation of inclusion/exclusion criteria.

After the above-mentioned procedures if the subject meets selection criteria, the following procedures will be carried out:

- randomization;
- administration of the study product (must be done within 3 hours after the randomization);
- recording AE and SAE;
- recording concomitant therapy.

4.3.4.2. Visit 2 (Day 3)

The following procedures will be carried out at the visit:

- blood sampling for measuring hsCRP, BNP and NT-pro-BNP;
- outcome registration;
- evaluation of vital signs (BP, HR, RR, body temperature);
- body weight measurement (for subjects who did not undergo measurement on Day 1);
- physical examination;
- recording AE and SAE;
- recording concomitant therapy.

For patients discharged on Day 2, the procedures of the Day 3 visit can be carried out ahead of schedule (on Day 2).

4.3.4.3. Visit 3 (Day 14±3)

The following procedures will be carried out at the visit:

- blood sampling for hematology and biochemistry, for measuring hsCRP, BNP and NT-pro-BNP;
- outcome registration;
- evaluation of vital signs (BP, HR, RR, body temperature);
- body weight measurement;
- height registration (it is permissible to record any value obtained during the hospitalization, when it was possible to measure the patient's height);
- physical examination;
- recording AE and SAE;
- recording concomitant therapy.

4.3.4.4. Visit 4 (Day 28±3)

The following procedures will be carried out at the visit:

CONFIDENTIAL

Translation dated 27-Oct-2021

based on Russian Version 4.0 dated 02-Oct-2021

Page 42 of 98

- blood collection for hematology and biochemistry, determination of hsCRP, BNP and NT-pro-BNP;
- outcome registration;
- evaluation of vital signs (BP, HR, RR, body temperature);
- physical examination;
- body weight measurement;
- Echo-CG;
- recording AE and SAE;
- recording concomitant therapy.

4.3.4.5. Visit 5 (Month 6±2 weeks)

The visit may be made by phone. The following procedures will be performed at the visit:

- outcome registration;
- recording AE and SAE;
- recording concomitant therapy.

4.3.4.6. Visit 6 (Month 12±2 weeks)

The following procedures will be performed at the visit:

- blood sampling for measuring BNP and NT-pro-BNP;
- outcome registration;
- evaluation of vital signs (BP, HR, RR, body temperature);
- physical examination;
- body weight measurement;
- Echo-CG;
- recording AE and SAE;
- recording concomitant therapy.

By the end of all visit procedures, the study will be considered as completed for the subject.

4.3.4.7. Unscheduled visits

The subjects may consult Investigator and make an unscheduled visit at any time in case they have adverse events or if, according to investigators, their condition requires medical intervention.

Investigator shall record the data into source medical documentation and the electronic Case Report Form (eCRF) (Unscheduled visit page). The following information should be added on an obligatory basis: visit date, visit reason, examination findings and data of additional investigations. If an AE was the reason of the visit or if an AE was revealed at unscheduled visit, recording of such AE shall be made using regular scheme (see Section 8).

After an unscheduled visit, the next visit shall be made according to the pre-established plan per Protocol.

4.3.4.8. Early withdrawal visits

In case of early withdrawal at the follow-up period post dosing (Visit 1 Day 1 – Visit 4 Day 28), an early withdrawal visit is advised including Visit 4 (Day 28±3) procedures:

- blood collection for hematology and biochemistry, determination of hsCRP, BNP and NT-pro-BNP;
- outcome registration;

CONFIDENTIAL

Translation dated 27-Oct-2021

based on Russian Version 4.0 dated 02-Oct-2021

Page 43 of 98

- evaluation of vital signs (BP, HR, RR, body temperature);
- physical examination;
- body weight measurement;
- Echo-CG;
- recording AE and SAE;
- recording concomitant therapy.

In case of early withdrawal during additional clinical follow-up period (Day 29 – Visit 6 Month 12), an early withdrawal visit is advised including Visit 6 (Month 12±2 weeks) procedures:

- blood sampling for measuring BNP and NT-pro-BNP;
- outcome registration;
- evaluation of vital signs (BP, HR, RR, body temperature);
- physical examination;
- body weight measurement;
- Echo-CG;
- recording AE and SAE;
- recording concomitant therapy.

4.4. Description of procedures and assessments

Periodicity of the procedures and assessments is also provided in Schedule of visits and procedures (see Table 1).

4.4.1. Demographic and other baseline assessments

At the screening (Day 1, baseline), the following data will be recorded:

- date of birth;
- sex;
- race.

4.4.2. Past medical history

At the screening (Day 1, baseline), the data on previous and concomitant diseases, surgeries and injuries will be collected. The following data will be recorded for female subjects: contraception method, menopause terms (if applicable) or causes for which she is considered infertile (see also Section 6.2.1.2.). The resulting data will be recorded in source medical documentation and in eCRF in section "Previous Diseases" and "Comorbidities".

4.4.3. Information on the underlying disease

At the screening (Day 1, baseline), the following data will be recorded:

- date and time of manifestations of ST-segment elevation myocardial infarction with which the patient is included in the study;
- results of 12-lead ECG based on which STEMI diagnosis was made (specifying the leads with elevated ST and extent of elevation in mm);
- date and time of CAG (specifying relevant findings based on its results), the fact of performing a PCI with stenting;
- history of MI (specifying the date) if any;
- diagnosis of chronic HF (specifying the date of diagnosis) if any.

The data obtained will be recorded in source medical documentation and eCRF.

CONFIDENTIAL

Translation dated 27-Oct-2021

based on Russian Version 4.0 dated 02-Oct-2021

Page 44 of 98

4.4.4. Pregnancy test

Urine pregnancy test will be performed by female subjects with retained childbearing potential at the screening (Day 1, baseline) using test strips. The data obtained will be recorded in source medical documentation and eCRF.

4.4.5. Efficacy assessment procedures

Efficacy assessment procedures will include:

- determination of hsCRP concentration;
- determination of concentration of HF biomarkers (BNP and NT-pro-BNP);
- echo-CG;
- outcome registration.

Description of procedures is provided in Section 7.2.

4.4.6. Safety cohort

Safety assessment procedures will include:

- evaluation of vital signs (BP, HR, RR and body temperature),
- physical examination (with obligatory assessment of injection site);
- hematology;
- biochemistry;
- AE/SAE recording.

Description of procedures is provided in Section 8.2.1.

4.5. Subjectivity minimization measures

4.5.1. Randomization

The subjects will be randomized in 1:1:1 ratio without stratification into one of treatment groups - RPH-104 80 mg, RPH-104 160 mg or placebo based on randomization scheme prepared using the relevant software by the responsible study statistician. Distribution will be made using block, non-adaptive, centralized randomization using Interactive Web Response System (IWRS).

At Visit 1 after eligibility of the patient is confirmed by the authorized blinded investigator, the unblinded investigator will perform randomization using the IWRS and obtain information about the patient's randomization number and assigned therapy group.

Detailed information on IWRS system will be presented in an individual IWRS manual kept in Trial Master File (TMF) and in each Investigator Site File (ISF).

The unblinded researcher will keep a register linking the screening and randomization numbers of study participants and therapy groups. Access to these registers for blinded employees will be limited.

Study participant randomization number may not be changed during the study. Distribution of the subject to a treatment group may not be changed during the study.

If the subject decides to refuse to participate or withdraw from the study for any reason, his/her randomization number may not be re-used.

Randomization scheme and identification of each subject will be added to the study report.

4.5.2. Blinding

The study will be double-blind, i.e. neither the physician (investigator) performing examination and follow-up, nor the subject will be aware of the treatment group to which the subject has been assigned and of the product administered. To assure double blind design, unblinded investigator's team and unblinded monitor will be involved. Detailed description of operational peculiarities will be presented in an individual Guidelines on medicinal product handling.

Given that administration of RPH-104 at 160 mg is only possible by two 80 mg injections (2 mL) at different sites and appearance of the finished forms of test product and placebo may differ, the following dosing regimen will be used to assure double blind design:

- in RPH-104 80 mg group, the subjects will receive 2 mL (80 mg) of RPH-104 and 2 mL of placebo on different administration sites;
- in RPH-104 160 mg group, the subjects will receive 2 mL (80 mg) of RPH-104 and 2 mL of (80 mg) of RPH-104 on different administration sites;
- in placebo group, the subjects will receive 2 mL of placebo and 2 mL of placebo on different administration sites.

Unblinded investigators will be aware of the treatment group from IWRS and perform administration of the study products.

Additional conditions limiting the subject's visual control will be enforced upon the study product administration.

Monitoring of this process on Sponsor's behalf will be made by unblinded monitor.

4.6. Storage of randomization/identification codes and their unblinding

The investigator should ensure confidentiality of the subjects. CRFs and other documents should only identify the subjects by their identification codes rather than by their names or surnames. In this study, the screening number is the patient's identification code. The screening number is assigned by the IWRS system after the patient has signed the ICF.

The blinded investigator must enter the patient's screening number in the source documentation and keep a separate screening and randomization log. The patient's screening number cannot be changed during the study.

The investigator should keep a special identification log/list of numbers, surnames, addresses and phones and numbers of medical documentation (if available).

Unblinding of the identification code of the subject is only possible with his consent verified in writing and/or for the sake of his life and health.

Until the end of the study, randomization plan will be kept by the responsible study statistician. Unblinded staff of the center should ensure that a clinical study participant receives the therapy matching the therapy group assigned by the IWRS system.

Unblinding randomization codes and treatment groups may be performed as agreed with Sponsor in case of urgency and/or SAEs. Treatment group unblinding will be performed by the unblinded investigator using the IWRS and the subject's identification number, according to the procedure described in an individual IWRS guideline.

4.7. List of data recorded directly in CRF

Electronic case report form (eCRF) shall be filled for each subject participating in the study including basic study-related data.

CONFIDENTIAL

Translation dated 27-Oct-2021

based on Russian Version 4.0 dated 02-Oct-2021

Page 46 of 98

All the information added to eCRF should comply with the one in source documents (medical treatment record, clinical record, laboratory test reports, Protocols and extracts from other examinations).

No data to be entered in eCRF without reflecting the same information in source documentation will be stipulated by the current study. All study-related data will be first recorded in source documentation and then in eCRF.

5. Selection and exclusion of the study subjects

5.1. Inclusion criteria

The subjects eligible for the study should meet all of the following criteria:

1. Subjects of either gender aged from 18 years old inclusive.
2. Subjects who gave voluntary written informed consent to participate in the study and to follow all Protocol procedures.
3. STEMI diagnosis defined as chest pain or its equivalent with ECG findings evidencing ST elevation (>1 mm) in two or more consecutive leads or LBBB according the investigator's judgement.
4. PCI with stenting was performed within no more than 12 hours after onset of chest pain or its equivalent and randomization was performed in no more than 12 hours after PCI (overall within 24 hours of onset of chest pain or equivalent).
5. Consent of female subjects with childbearing potential defined as all female subjects with physiological potential to conceive, to use highly effective contraceptive methods throughout the study starting from screening (signing informed consent) and negative pregnancy test.

Highly effective contraceptive methods include combination of two of the following methods (a+b or a+c or b+c):

- a) oral, injection or implanted hormonal contraceptives; in case of oral contraceptives, the female subjects should administer the same product for at least 3 months prior to the study therapy;
- b) intrauterine device or contraceptive system;
- c) barrier methods: condom or occlusive cap (diaphragm or cervical cap/vaginal fornix cap) with spermicidal foam/gel/film/cream/vaginal suppository.
6. Ability and willingness of the subject, according to the reasonable investigator's judgment, to attend the study site at all scheduled visits, undergo the study procedures and follow the Protocol requirements including subcutaneous injections by qualified site personnel.

5.2. Non-inclusion criteria

The subjects meeting any of exclusion criteria should not be enrolled:

1. Hypersensitivity to test product (RPH-104) and/or its ingredients/excipients.
2. Pregnancy and breastfeeding.
3. Verified chronic HF (AHA/ACC C-D class, NYHA FC III-IV).
4. Pre-existing severe valvular heart disease according to the investigator's assessment.
5. Pre-existing LV dysfunction (EF<40%).
6. History of STEMI.

CONFIDENTIAL

Translation dated 27-Oct-2021

based on Russian Version 4.0 dated 02-Oct-2021

Page 47 of 98

7. Complications of acute MI in the form of acute left ventricular failure and cardiogenic shock defined as stable blood pressure decrease (SBP<90 mm Hg) associated with signs of hypoperfusion as well as cases when inotropic and/or mechanical support is required to maintain SBP; and/or unstable hemodynamics.
8. Active infections (acute or chronic); active tuberculosis.
9. Recent (less than 5 half-life periods) or current administration of colchicine, as well as agents with an immunosuppressant mechanism of action, including, but not limited to: glucocorticoids at doses of > 1 mg/kg of methylprednisolone equivalent, tumor necrosis factor-alfa (TNF α) blockers, IL-1 and other biological drugs, cyclosporine and other immunosuppressants. The use of non-steroidal anti-inflammatory drugs (NSAIDs) are allowed.
10. Immunization with live vaccines within 90 days prior to the study product administration.
11. Chronic systemic autoimmune or autoinflammatory diseases.
12. Suspected necessity in cardiosurgery.
13. Oncology (or diagnosis of oncology within the last 5 years).
14. History of organ transplantation or necessity in transplantation at the screening initiation or scheduled transplantation during the study.
15. Neutropenia (absolute neutrophil count <1800/mm³).
16. Participation in another clinical study within the previous 3 months prior to Screening visit.
17. Other medical (including mental) conditions or abnormal laboratory findings which may increase the risk for the subject associated with the study participation or administration of the study products or which may affect interpretation of the study results and, according to the investigator, render the subject ineligible for the study. *
18. The subjects working at the study site or subjects working for Sponsor directly involved in this clinical study.

**If, in the Investigator's opinion, administration of a non-live COVID-19 (SARS-CoV-2) vaccine increases the risk for the patient related to his/her participation in the study, the Investigator can make a decision not to include this patient into the study.*

Presence of neutropenia for evaluation of exclusion criteria will be performed based on hematology performed at the study site local laboratory.

5.3. Deviations from inclusion/exclusion criteria

No deviations from the inclusion/exclusion criteria are permitted. The investigator can call the study's medical monitor to discuss eligibility for any study participant.

5.4. Study termination or suspension, early withdrawal criteria

5.4.1. Study termination criteria.

Sponsor and principal investigator will have the right to terminate or suspend the study at any time for the reasons including (but not limited to) safety issues, ethical issues or major Protocol violations, lack of achievement of the study purposes or for other reasons.

Particularly, the study will be terminated early or suspended in the following cases:

- at Sponsor's initiative;
 - a) upon receipt of new toxicological or pharmacological data or data concerning SAEs requiring revision of earlier evaluation of risk-benefit ratio for participation in the study;

CONFIDENTIAL

Translation dated 27-Oct-2021

based on Russian Version 4.0 dated 02-Oct-2021

Page 48 of 98

- b) frequency of AEs and/or their severity do not allow to continue the study;
- c) other reasons including administrative ones;
- at investigator's initiative: frequency of AEs and/or their severity unacceptably increases the risk for the study subjects.
- at the decision of regulatory authorities.

At that, Sponsor shall notify Investigator or management of medical facility on early discontinuation/suspension of the study in writing.

If the study will be terminated/suspended for safety reasons, Sponsor shall immediately report this to the investigators as well as to regulatory authorities and ethics committees.

Where the investigator terminates the study before its termination at the study site, he/she should notify Sponsor immediately and provide the reasons.

Regulatory authorities or ethics committees will be entitled to terminate the study for the reasons including (but not limited to) safety issues according to the current local regulatory requirements.

5.4.2. Early withdrawal criteria

The subject may withdraw the study at any time before its termination (Visit 6). The investigator may also decide to withdraw a subject at his/her own discretion.

The reasons for study withdrawal will be reflected in source medical documents and eCRF and may include the following:

1. Recall of informed consent to participate in the study.
2. Serious or intolerable AE requiring withdrawal from the study at the investigator's discretion.
3. Investigator's decision that continuation of the study participation contradicts the subject's interests.
4. Investigator's decision if the subject does not follow the study procedures and/or Protocol.
5. Protocol deviation which, according to the investigator, requires early subject withdrawal from the study (e.g. necessity or performance of additional therapy forbidden by the Protocol). In this case, decision on the subject withdrawal will be agreed with Sponsor.
6. Study termination by Sponsor.
7. Study termination by regulatory authorities.
8. Pregnancy of the subject.
9. Death of the subject.

5.4.3. The list of data by early withdrawn subjects and terms of their collection

In case of early withdrawal, justification of such decision and its reason should be specified in source medical documents and eCRF.

Where a subject recalls his/her informed consent, the investigator should try to learn the cause of such a decision.

In case of early withdrawal at the follow-up period post dosing (Visit 1 Day 1 – Visit 4 Day 28) an early withdrawal visit is advised including Visit 4 procedures.

In case of early withdrawal during additional clinical follow-up period (Day 29 – Visit 6 Month 12) an early withdrawal visit is advised including Visit 6 procedures.

5.4.4. Replacement of withdrawn subjects and accounting of their data

The subjects withdrawn will not be replaced.

CONFIDENTIAL

Translation dated 27-Oct-2021

based on Russian Version 4.0 dated 02-Oct-2021

The data of the subjects withdrawn before randomization will be taken into account in the study report in subject disposition analysis only. The data from the subjects withdrawn post randomization will be taken into account in the final analysis in the relevant set (see Section 9).

5.4.5. Follow-up of withdrawn subjects

Follow-up of the subjects withdrawn due to a SAE will be performed until its resolution or stabilization.

The subjects withdrawn for other reasons will not be followed.

6. Treatment of the study subjects

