4.3.2. Treatment period

The day of treatment initiation will coincide with the day of screening, treatment period will include single administration of the study products.

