7.1. List of efficacy parameters

Primary endpoint

1. hsCRP area under curve (AUC) from Day 1 (baseline) until Day 14 [Visit 1 Day 1 – Visit 3 Day 14].

Secondary endpoints

1. hsCRP area under curve (AUC) from Day 1 baseline) until Day 28 [Visit 1 Day 1 – Visit 4 Day 28].
2. BNP area under curve (AUC) from Day 1 (baseline) until Day 28 [Visit 1 Day 1 – Visit 4 Day 28].
3. NT-pro-BNP area under curve (AUC) from Day 1 (baseline) until Day 28 [Visit 1 Day 1 – Visit 4 Day 28].
4. Incidence of fatal outcomes (cardiac and non-cardiac) during 12-month follow-up period [Visit 1 Day 1 – Visit 6 Day 365].
5. Incidence of hospitalizations due to HF or other cardiac reasons not associated with HF, or due to non-cardiac reasons during 12-month follow-up period [Visit 1 Day 1 – Visit 6 Day 365].
6. Incidence of new cases of HF (defined as hospitalization due to HF or new onset of HF) during 12-month follow-up period [Visit 1 Day 1 – Visit 6 Day 365].
7. Incidence of “fatal outcome (due to any reason) or hospitalization due to HF or new onset of HF” Frequency of fatal outcomes for any cause OR hospitalization for HF OR the development of HF in the outpatient settingsduring 12-month follow-up period [Visit 1 Day 1 – Visit 6 Day 365].
8. Incidence of “fatal outcome (due to any reason) or hospitalization due to HF” during 12-month follow-up period [Visit 1 Day 1 – Visit 6 Day 365].

- 9. 9. Changes in levels of BNP and NT-pro-BNP during 12-month follow-up period compared to baseline [Visit 1 Day 1 – Visit 6 Day 365].
- 10. Changes in structural and functional echocardiographic parameters after 12 months compared to baseline [Visit 1 Day 1 – Visit 6 Day 365].

Exploratory endpoints

- 1. Changes in concomitant therapy [Visit 1 Day 1 – Visit 6 Day 365].
- 2. Interaction between STEMI outcomes and peculiarities of coronary bed lesion based on baseline CAG results [Visit 1 Day 1 – Visit 6 Day 365].

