8.2.6. Serious adverse event reporting

To assure safety of the subjects in case of any SAE development after signing ICF and until the end of the study, regardless of suspected causes of SAE or association with the study product, SAE should be reported to Sponsor within 24 hours after the investigator became aware of the SAE.

If a subject has a SAE considered to be related to the study product, a report thereof should be submitted even in case the study has been terminated already.

Filling serious adverse event report form

SAEs should be reported by filling out the SAE page in the eCRF within 24 hours from the time the investigator finds out about the SAE. In the event that access to the eCRF is temporarily impossible, the center has the opportunity to report the SAE by sending a scan of the hard copy of the serious adverse event report by email to

[contact]

or by [contact]

The investigator must notify the Local Ethics Committee (LEC)/Institutional Review Board (IRB) on the SAE according to LEC/IRB standard operation procedures.

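### Section 5.4.5 stops follow-up at withdrawal after a single Day 1 dose, so 12-month deaths, hospitalisations and heart failure (secondary endpoints 4-8) are not actively collected from withdrawn subjects who still consent

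*Combined protocol and SAP*

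**What the plan says.** - **Dosing (4.3.2).** The "treatment period will include single administration of the study products", on the day of screening.
- **Withdrawal (5.4.2).** The listed reasons include recall of consent, but also several that need none: a serious or intolerable adverse event (AE), forbidden therapy, pregnancy, the subject's interests as the investigator sees them, and "Investigator's decision if the subject does not follow the study procedures and/or Protocol".
- **Follow-up after withdrawal (5.4.5).** "Follow-up of the subjects withdrawn due to a SAE will be performed until its resolution or stabilization". Then: "The subjects withdrawn for other reasons will not be followed".
- **Withdrawal visit (5.4.3 and 4.3.4.8).** Up to Day 28, "an early withdrawal visit is advised including Visit 4 procedures". After that, Visit 6 procedures are advised. Both include outcome registration.
- **Endpoints (7.1).** Endpoint 4 is "Incidence of fatal outcomes (cardiac and non-cardiac) during 12-month follow-up period". Endpoints 5-8 (hospitalisation, new HF and two composites) have the same window, to Day 365.
- **Analysis (5.4.4 and 9.3.3.2).** "The data from the subjects withdrawn post randomization will be taken into account in the final analysis", in the relevant set. Endpoints 4-8 are shown as proportions of FAS subjects and as a valid percentage that is not defined, and are compared by Fisher's exact test.

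**The concern.** With a single dose there is no later treatment to stop, so withdrawal after Day 1 ends only data collection. A subject withdrawn at Month 3 for missed procedures may be willing to take a telephone call at Month 12, yet the plan does not make it. If that subject later dies or is admitted with HF, the event is not sought. The subject still sits in the FAS denominator, where an unknown status counts as no event.

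Endpoints 4-8 are the direct evidence on objective 3, clinical outcomes within 12 months. Section 9.1 leaves last observation carried forward to the SAP, but no analysis rule can recover an event that was never collected. With 34 subjects per arm, each unknown status is visible in the result.

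**Working it through.** **1. The plan's own figures.** Section 9.4 claims power above 90% with 34 per arm at a standardised effect of 0.80, and above 80% after 20% loss. A two-sample t calculation gives 0.902 with 34 per arm and 0.822 with 27 per arm (34 x 0.8 = 27.2). Both claims reproduce. They concern hsCRP AUC to Day 14, so this point does not touch them.

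**2. Does another section supply the missing outcomes?**
- The withdrawal visit is advised only, and registers events up to that visit.
- Section 8.2.4 ends SAE recording 30 days after treatment or at the last visit, whichever is later.
- Section 8.2.6 requires reporting of "any SAE development after signing ICF and until the end of the study", within 24 hours of the investigator becoming aware. It does not require anyone to look.
- Section 8.2.12 monitors AEs that already exist.
- The outcome committee (9.8) classifies what reaches it.
- Sponsor agreement to withdrawals (10.4) may reduce their number but collects no data.
- Section 8.2.13 records pregnancy outcome even after withdrawal, so the protocol already accepts post-withdrawal collection for one outcome.

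None of these gives outcome follow-up to Day 365.

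**3. Bound without a model for event timing.** From the documents: 34 per arm. Assumed: 5-20% withdrawal by Day 365. The 20% in 9.4 belongs to the hsCRP power statement.
- One unknown status: 1/34 = 2.9 percentage points.
- 5%: 34 x 0.05 = 1.7, about 2 subjects; 2/34 = 5.9 points.
- 20%: 34 x 0.20 = 6.8, about 7 subjects; 7/34 = 20.6 points.

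These are the widest possible additions to the range of an arm's risk.

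**4. Expected loss under a simple model.** Assumed: true 12-month risk p = 0.20; share e = 0.6 of events spread evenly over days 0-90 and the rest over days 90-365; withdrawal fraction w, unrelated to prognosis and spread evenly over the year; all 102 subjects in the FAS. For scale only, section 2.1 cites HF in more than 20% within 90 days after MI. This trial excludes acute left ventricular failure, so its rate may be lower.

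Mean share of a withdrawn subject's events falling before withdrawal:

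F = [90 x e/2 + 275 x (1 + e)/2] / 365 = (27 + 220)/365 = 0.677

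FAS percentage = p[1 - w(1 - F)]. Uncollected events = 102 x w x p x (1 - F). Expected total = 102 x 0.20 = 20.4.

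| w | FAS percentage | Uncollected events |
|---|---|---|
| 5% | 19.7% | 0.33 |
| 10% | 19.4% | 0.66 |
| 20% | 18.7% | 1.32 |

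**5. Sensitivity at w = 20%.**
- e = 0.4 gives F = 0.577, FAS 18.3% and 102 x 0.20 x 0.20 x 0.423 = 1.7 events. e = 0.8 gives F = 0.777, FAS 19.1% and 0.9 events.
- Stress case, all withdrawals within 28 days: F = 0.6 x 14/90 = 0.093, FAS 16.4%, 3.7 events uncollected. If events to day 30 are captured under 8.2.4, F = 0.6 x 30/90 = 0.200, FAS 16.8%, 3.3 events. Nothing in the documents suggests this pattern.
- If only half of those withdrawn still consent (assumed), 0.33-1.32 events become about 0.2-0.7.

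**The case against.** **The figures count too much.** They cover every withdrawal. Section 5.4.2 also lists recall of consent, termination by the sponsor or regulator, and death. A death is itself endpoint 4 and is known; a subject who refuses all contact cannot be recovered. This stands: the numbers are upper limits on what the fix could recover, and the recoverable share is not in the documents.

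**One illustration stands for five endpoints.** Section 2.1 cites in-hospital mortality of 4-12% against about 10% at 12 months, and the footnote to 7.2 counts HF within 24 hours of index admission. Both suggest early events, before most withdrawals. This also stands. It argues for a smaller loss, not for none.

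**Loss can be examined in part.** A reader might infer that the collected data could not show whether loss tracks prognosis. That is too strong. Withdrawal reasons are recorded (5.4.2) and tabulated (9.3.1), and the advised visit takes natriuretic peptides, echocardiography and outcomes. The evidence is partial, because the visit is optional and nothing is known afterwards.

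**Sections 5.4.5 and 8.2.6.** These might look contradictory. They are compatible: reporting an SAE one learns of does not require active follow-up. The real conflict is with 8.2.12, which has all AEs monitored until resolution or stabilisation, while 5.4.5 stops follow-up of a subject withdrawn for an intolerable but non-serious AE.

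**The study is exploratory.** Phase 2a, no power claim for endpoints 4-8, primary endpoint untouched. This limits the priority. It is not a reason to leave obtainable outcomes uncollected.

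**Conclusion.** The point holds as a design weakness of modest size. Followed as written, 5.4.5 leaves 12-month outcomes uncollected in withdrawn subjects who still consent, and no other section closes the gap. At 20% true risk and 5-20% withdrawal spread over the year, about 0.3-1.3 of 20 events are lost and the FAS shows 19.7-18.7%. Both rates are assumed, every withdrawal is counted, and withdrawal is taken as unrelated to prognosis.

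A reader might infer that the treatment comparison is biased. The documents do not support that: nothing in them indicates that withdrawal would differ by arm. Single events can move Fisher's test (10/34 against 2/34 gives p = 0.023; 10/34 against 4/34 gives p = 0.132). But two unseen events confined to one arm is a constructed case. The illustration expects 0.33/3 = 0.11 to 1.32/3 = 0.44 per arm.

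Confidence is high on the reading of 5.4.5 and low on the exact size. The change is worth making because it is cheap.

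**What to change.** - **Section 5.4.5.** Keep every subject withdrawn after randomisation who has not withdrawn consent to follow-up in outcome registration (vital status, hospitalisation, HF) by telephone call at Month 6 and Month 12. The protocol already allows a call in place of attendance at Visit 5. Leave the SAE sentence in place.
- **Records.** Request hospital records for reported events, so that the outcome committee can classify them against Appendix 1.
- **Consent form.** Add a line that separates stopping visits from stopping follow-up.
- **Reporting.** Show the number with unknown Day-365 status by arm and reason. In the SAP, define the valid percentage and state which denominator Fisher's test uses.
- **Reconcile** 5.4.5 with 8.2.12 on AE monitoring after withdrawal.

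**Cost.** A protocol amendment and consent-form change with ethics and regulatory approval (section 14), possibly with re-signature by enrolled subjects. Up to two calls for each of about 5 to 20 withdrawn subjects (5% to 20% of 102, assumed), plus record retrieval for the few events reported. Subjects who refuse contact remain unknown.
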